## 1. PROTOCOL SUMMARY

The study is conducted in accordance to the requirement of global multi-center study, ENABLE MRI (NCT02652481), on MR conditional systems including DYNAGEN and INOGEN. MR ICD (Magnetic Resonance - Implanted Cardiac Devices) protocol is based on ENABLE MRI study. National Medical Products Administration (NMPA) requires certain clinical trial in China to support the approval of ImageReady™ MR conditional defibrillation system. The ImageReady MR Conditional Defibrillation System included in the MR ICD Clinical Study, here to forward referred to as the ImageReady System, consists of DYNAGEN and INOGEN series pulse generators, RELIANCE 4-FRONT series defibrillation leads, ACUITY X4 series left ventricle (LV) leads, and INGEVITY series pacing leads for right atrium (RA).

### ***1.1 Study design:***

This is a prospective, multi-center, single-arm, pre-market study

### ***1.2 Study objective:***

The study objective is to evaluate the safety and effectiveness of ImageReady™ MR conditional defibrillation system in Chinese population, to support the regulatory approval by NMPA.

### ***1.3 Number of sites and patients and enrollment***

Subjects in this trial will not be randomized. Subjects will be considered enrolled into the MR ICD study at the time of informed consent form execution. All subject enrollments will be counted against the enrollment ceiling for the study.

This study will be conducted at up to 5 centers in China. Data will be collected at 20 patients. All participating patients will sign the informed consent form approved at the participating center per local requirements. Generally, one individual center may not enroll more than 10 subjects. Investigational sites will be notified when the enrollment goal is close to being reached and once enrollment is complete.

### ***1.4 Description of study population***

Subjects enrolled in the MR ICD study shall be selected from the investigators general patient population indicated for an ICD or CRT-D implantation. The Investigator is responsible for screening potential subjects and selecting those who meet the eligibility criteria for the study as described in Inclusion and Exclusion criteria.

### ***1.5 Description of device(s) including model numbers used in the study***

The ImageReady MR Conditional Defibrillation System included in the MR ICD Clinical Study, here to forward referred to as the ImageReady System, consists of DYNAGEN and INOGEN series pulse generators, RELIANCE 4-FRONT series

defibrillation leads, ACUITY X4 series left ventricle (LV) leads, and INGEVITY series pacing leads for right atrium (RA). DYNAGEN and INOGEN pulse generators, belonging to the new generation products. DYNAGEN will be used as the only pulse generator in MR ICD study, while lead selection will be decided mainly by investigators based on subjects' anatomy and clinical practice. This study intention is to label the ImageReady MR Conditional Defibrillation System models "MR Conditional" as defined by the American Society for Testing and Materials (ASTM) 3, when used as a system and in accordance with labeled Conditions of Use.

The below table give the details of ImageReady MR Conditional Defibrillation System Components

Component	Name	Model	Features
Pulse Generators	DYNAGEN	D150	Single chamber ICD, DF4
		D152	Dual chamber ICD, DF4
		G158	CRT-D, DF4, IS4
	INOGEN	D140	Single chamber ICD, DF4
		D142	Dual chamber ICD, DF4
		G148	CRT-D, DF4, IS4
Defibrillation Leads	RELIANCE 4-FRONT active fixation, single coil, Gore coating	0692	59cm
		0693	64cm
		0657	70cm
	RELIANCE 4-FRONT active fixation, dual coil, Gore coating	0695	59cm
		0696	64cm
		0658	70cm
	LV leads	4671	86cm
		4672	95cm
		4674	86cm
		4675	95cm
RA leads	ACUITY X4 straight	4677	86cm
		4678	95cm
	ACUITY X4 spiral S	7735	45cm
		7736	52cm
	ACUITY X4 spiral L	7740	45cm
		7741	52cm
	INGEVITY passive fixation, J type	7742	59cm
		7731	52cm
		7732	59cm

### ***1.6 Study procedure***

Data will be collected from subjects upon enrollment into the study, at implant, and at pre-discharge. Subjects will have an MR scan at 6-9 weeks post-implant, or at least 6 weeks after any required surgical interventions to the ImageReady System (labeled as MRI Visit). Subsequently, there will be a clinic follow up at MRI + 1 Month Visit, and recommended clinic follow up every 3 months post MR scan. Subjects will also be followed at 1-year post-implant. The MR ICD study is composed of two phases. Phase I is completed when all the subjects finish MRI + 1 Month Visit, which starts Phase II till 1-year post implantation. The first Every 3-month visit will occur  $90 \pm 14$  days after MRI visit. Subsequent Every 3-month follow-up visits will be scheduled every three months ( $90$  days  $\pm 14$  Days) from the previous scheduled study follow-up. Phase I is expected to last about 9 months after first subject enrollment, and the whole study is expected to last about 20 months after first subject enrollment.

### ***1.7 Follow-up schedule***

After First MRI visit the patient visit include:

- a. MRI + 3month visit
- b. MRI + 6month visit
- c. MRI + 9month visit
- d. Implant+ 1-Year visit
- e. Medically necessary MRI
- f. Any Additional visits

Subject data will be recorded in a limited access secure electronic data capture (EDC) system. The individual subject will finish the study when he/she completes the Implant + 1 Year Visit.

### ***1.8 Study duration***

Phase I is expected to last about 9 months after first subject enrollment, by when all the subjects will have finished MRI +1 Month Visit. Phase II continues to all the subjects complete one-year follow-up post-implant, and the whole study is expected to last about 20 months after first subject enrollment. Statistical analysis reports are also generated based on Phase I and Phase II study durations. (See [section 5.1](#))

## 2. INTRODUCTION

This statistical analysis plan addresses the planned analyses for the MR ICD CHINA-Clinical Trial based on the latest version of protocol dated May 1, 2018, Version AC. Specified analyses may be used for scientific presentations and/or manuscripts, and regulatory submissions.

Subjects depending on the implanted leads will be performed :

- a. Manual Right Atrial Threshold Test
- b. Manual Right Ventricular Threshold Test
- c. Manual Left Ventricular Threshold Test

Upon the completion of Implant procedure, Pre-discharge Visit will occur either on the same day as the ImageReady System implant procedure, a minimum of 3 hours after pocket closure, or up to 72 hours after the implant procedure. Then MRI visits and other follow-up visits will occur.

The primary safety analysis will be based on MR Scan-related ImageReady System Complication-Free Rate between the MR Scan and the MRI + 1 Month Visit. The primary effectiveness endpoints based on Abnormal increase and decrease in RV and LV on impedance, threshold and amplitude. Ancillary components RA & IV assessments, VT/VF episodes assessments and Image Artifacts assessments will be analyzed as well. These analyses are more elaborately detailed in the below endpoint analysis.

## 3. ENDPOINT ANALYSIS

The primary safety endpoint analysis is based on MR Scan-Related ImageReady System Complication Free Rate.

### 3.1 Primary Safety Endpoint

- i. Primary Safety Endpoint: The primary safety endpoint of the MR ICD study will be assessed for all subjects who undergo any portion of the study-required MR scan sequences. Safety will be confirmed by evaluating the MR scan related ImageReady System complication-free rate (CFR) between the MR Scan and the MRI Visit + 1 Month. There is no hypothesis testing in the MR ICD study, and it can be considered reasonable if up to 2 failed cases of primary safety endpoint event may occur. Descriptive statistics will be conducted for the endpoint events with 95% CI. The time window for MRI + 1 Month visit is 30±7 days post MR scan, so it will*

*capture events within at least 23 days post scan. Missing data will be excluded.*

### **3.2 Primary Efficacy Endpoint**

*There are 5 primary effectiveness endpoints on the Abnormal increase and decrease in RV and LV components for shocking impedance, pacing threshold and sensed amplitude. There is no hypothesis testing in the MR ICD study, and it can be considered reasonable upon the failed cases of primary effectiveness endpoint occur.*

#### **i. Primary Effectiveness Endpoint 1: Pre-MR Scan vs. 1 Month Post-MR Scan RV shocking impedance:**

*The data set for the primary effectiveness endpoint 1 will only include subjects who undergo the study-required MR scan and complete all the sequences, and will not include subjects that meet any of the following exclusions:*

- *Has a medically necessary scan between implant and the MRI + 1 Month Visit*
- *Fails to meet labeled MRI Conditions of Use*
- *Experiences a lead-related complication between MRI Visit and the MRI + 1 Month Visit*

The normal RV shocking impedance measured by the system should be  $\leq 200$  Ohm, with  $>200$  Ohm considered abnormal. The primary effectiveness endpoint 1 is defined as that the average RV shocking impedance is  $>200$  Ohm 1-month post scan, while it is  $\leq 200$  Ohm before scan.

#### **ii. Primary Effectiveness Endpoint 2: Pre-MR Scan vs. 1 Month Post-MR Scan RV Pacing Threshold at 0.5 ms:**

*The data set for the primary effectiveness endpoint 2 will only include subjects who undergo the study-required MR scan and complete all the sequences, and will not include subjects that meet any of the following exclusions:*

- *Has a medically necessary scan between implant and the MRI + 1 Month Visit*
- *Fails to meet labeled MRI Conditions of Use*
- *Experiences a lead-related complication between MRI Visit and the MRI + 1 Month Visit*

The primary effectiveness endpoint 2 is defined as ‘an increase in average pacing thresholds  $\leq 0.5V$  (at 0.5 ms) from pre-MR Scan to MRI Visit + 1

Month follow-up will be considered as success', otherwise it's a failure (event).

iii. **Primary Effectiveness Endpoint 3: Pre-MR scan vs. 1 Month Post-MR Scan RV Sensed Amplitude:**

*The data set for the primary effectiveness endpoint 3 will only include subjects who undergo the study-required MR scan and complete all the sequences, and will not include subjects that meet any of the following exclusions:*

- *Has a medically necessary scan between implant and the MRI + 1 Month Visit*
- *Fails to meet labeled MRI Conditions of Use*
- *Experiences a lead-related complication between MRI Visit and the MRI + 1 Month Visit*
- *Average RV sensed amplitude <5mV pre-MR scan*

The primary effectiveness endpoint 3 is defined as 'an increase in average pacing thresholds  $\leq 0.5V$  (at 0.5 ms) from pre-MR Scan to MRI Visit + 1 Month follow-up will be considered as success', otherwise it's a failure (event).

iv. **Primary Effectiveness Endpoint 4: Pre-MR Scan- vs. 1 Month Post-MR Scan LV Pacing Threshold at 0.5 ms:**

*The data set for the primary effectiveness endpoint 4 will only include subjects who undergo the study-required MR scan and complete all the sequences, and will not include subjects that meet any of the following exclusions:*

- *Has a medically necessary scan between implant and the MRI + 1 Month Visit*
- *Fails to meet labeled MRI Conditions of Use*
- *Experiences a lead-related complication between MRI Visit and the MRI + 1 Month Visit*

The primary effectiveness endpoint 4 is defined as 'increase in average pacing thresholds  $\leq 1.0V$  (at 0.5 ms) from pre-MR Scan to MRI Visit + 1 Month follow-up will be considered a success', otherwise it's a failure (event).

v. **Primary Effectiveness Endpoint 5: Pre-MR scan vs. 1 Month Post-MR Scan LV Sensed Amplitude:**

*The data set for the primary effectiveness endpoint 5 will only include subjects who undergo the study-required MR scan and complete all the*

*sequences, and will not include subjects that meet any of the following exclusions:*

- *Has a medically necessary scan between implant and the MRI + 1 Month Visit*
- *Fails to meet labeled MRI Conditions of Use*
- *Experiences a lead-related complication between MRI Visit and the MRI + 1 Month Visit*
- *Average LV sensed amplitude <5mV pre-MR scan*

### **3.3 Ancillary Assessments**

*The ancillary endpoints are not formal endpoints*

- Changes in RV and LV impedances pre-MR scan versus 1 Month post-MR scan (MRI Visit and MRI + 1 Month Visit) assessed for RV and LV Impedances
- Changes in RA lead measurements including pacing thresholds, sensed amplitudes and impedances, between pre- and 1 Month post-MR scan measurements assessed for RA lead measurements
- The detection time (first elapsed time), therapy given and conversion result, shocking impedance (if applicable) assessed for post MR scan VT/VF episodes. For a VT/VF episode, there might be no therapy, ATP or Shock therapy. Only shock therapy will have a shocking impedance, while shock for VT/VF might be very few in this small sample study. Data collected from Arrhythmia Logbook Report used for Assessment of VT/VF post MR scan and only VT/VF episodes from Arrhythmia log book considered for analysis. Detection time, Therapy given are summarized based on subject total episodes from visit and shocking impedance summarized based on subjects.
- The following information will be summarized for both study-related MR scans and medically necessary MR scans:
  - Duration of the PG in the MRI Protection Mode
  - Time from the start of the MRI Protection Mode to the start of the MR scan
  - Time from the end of the MR scan to exiting the MRI Protection Mode
- MR image quality scores will be presented in study report for assessment of Image Artifacts for non-medically necessary MR scans

### **3.4 Hypotheses**

There is no formal hypothesis planned for this study. The individual performance goal is sort of hypothesis, to decide the performance status of each endpoint.

### 3.5 Sample Size

The MR ICD study is a small sample size study without any formal hypothesis testing. Twenty subjects (10 with ICD and 10 with CRT-D) will be enrolled. It is assumed that the attrition should not be more than 2 cases in each group, so that at least 8 ICD subjects (at least 1 single chamber and 1 dual chamber ICD) and 8 CRT-D subjects shall undergo required MR scan and complete all the sequences. Sample size might be expanded to meet this assumption.

### 3.6 Statistical Methods

The procedure success rate for both primary safety and efficacy endpoints will be summarized descriptively. Categorical variables will be tabulated with frequencies, percentages and 95% confidence intervals. Continuous variables will be tabulated with mean, median, standard deviation, minimum, maximum, and 95% confidence interval of the mean.

#### **4.2 Control of Systematic Error/Bias**

There is no randomization schema assigned in the study. Selection of patients will be made from the Investigator's usual patient load. All patients meeting the eligibility criteria and having signed the ICF will be eligible for enrollment in the study. An independent Clinical Events Committee (CEC) will determine the MR Scan-related ImageReady System complications. Consecutively eligible subjects should be enrolled into the study to minimize selection bias.

#### **4.3 Number of Subjects per Investigative Site**

The study will be conducted in approximately 5 sites and one single site may not enroll more than 10 subjects.

### **5. DATA ANALYSES**

#### **5.1 Endpoints/Measurements analysis**

Statistical endpoint and other analysis report generated based on study design phases, which as detailed in study duration section. Phase I include the statistical report till 9 months study duration and Phase II statistical report for complete study including all follow-ups and additional visits information. A set of additional tables and listings will be provided based on final available data lock, compared to initial Phase I generated report. However, this analysis plan created in context to final statistical report.

### 5.1.1 Primary efficacy endpoint analysis:

The primary effectiveness endpoints are defined as ‘a success based on the specified criteria conditions earlier’, otherwise it’s a failure (event) .

All the 5- primary endpoints are based on Implant population,

- Pre-MR Scan vs. 1 Month Post-MR Scan RV shocking impedance
- Pre-MR Scan vs. 1 Month Post-MR Scan RV Pacing Threshold at 0.5 ms
- Pre-MR scan vs. 1 Month Post-MR Scan RV Sensed Amplitude
- Pre-MR Scan- vs. 1 Month Post-MR Scan LV Pacing Threshold at 0.5 ms
- Pre-MR scan vs. 1 Month Post-MR Scan LV Sensed Amplitude

are summarized descriptively with counts and percentages presenting 95% Clopper-Pearson confidence interval with two-sided exact binomial confidence bound at 95% will be presented to anticipate that the endpoint success is more than the lower bound of the confidence limits.

The time window for MRI + 1 Month visit is  $30\pm 7$  days post MR scan, so it will capture events within at least 23 days post scan for all the endpoints and Missing data will not be considered in the denominator part while deriving confidence limits and performance goals.

### 5.1.2 Primary safety endpoint analysis:

The primary safety endpoint of the MR ICD study will be assessed for all subjects who undergo any portion of the study-required MR scan sequences. Safety will be confirmed by evaluating the MR scan related ImageReady System complication-free rate (CFR) between the MR Scan and the MRI Visit + 1 Month. This endpoint is analyzed based on Implant population. Counts and percentages presenting 95% Clopper-Pearson confidence interval with two-sided exact binomial confidence bound at 95%.

Complications that are determined to be associated with the MR scan will be considered MR scan-related complications and count against this endpoint. Complication is defined as serious adverse event or permanent loss of device functions (pacing/defibrillation).

All the primary efficacy endpoint and safety endpoint been summarized presenting 95% Clopper-Pearson confidence interval with two-sided exact binomial confidence made for both Intent and Implant study populations. If subject’s status been categorized to either Attempt or Partial Implant, then the results been presented for both these populations as well.

### 5.1.3 *Ancillary Assessments*

We are also analyzing the ancillary assessments for pacing threshold, Pulse width, sensed amplitude and pacing impedance for RA, RV and LV components. The ancillary endpoints are not formal endpoints; however, we present results based on [Ancillary Assessments](#) requirements. A listing will be provided with all the details provided from the Arrhythmia log book.

All the categorical response of the measurements summarized using counts and percent. The continuous parameters including time variables presented with mean, standard deviation with counts and minimum and maximum values. is based on Implant population

We are also presenting the plots in connection with ancillary assessments for pacing threshold, Pulse width, sensed amplitude and pacing impedance for RA, RV and LV components.

- A mean plot generated based on the duration and pacing threshold by RA, RV and LV components by separate panel.
- A mean plot generated based on the duration and Pulse width by RA, RV and LV components by separate panel.
- A mean plot generated based on the duration and Sensed amplitude by RA, RV and LV components by separate panel.
- A mean plot generated based on the duration and Pacing impedance by RA, RV and LV components by separate panel.

### 5.1.4 *Interim Analyses*

No formal interim analyses are planned for this study. If the study is terminated prematurely, the already collected data shall be described according

### 5.1.5 *Subgroup Analyses*

No subgroup analyses are planned for this study. There is no formal subgroup analysis in the MR ICD study, however, descriptions may be grouped on study site, subject sex, device type (single chamber ICD, dual chamber ICD and CRT-D), etc.

### 5.1.6 *Justification of Pooling*

This study will be conducted under a common protocol for each investigational site with the intention of pooling the data for analyses. Every effort will be made to promote consistency in study execution at each investigational site.

### **5.1.7 Multivariable Analyses**

No multivariate methodology included for the primary, secondary or other endpoints

## **5.2 General considerations**

All continuous measurements will be summarized descriptively at each visit by treatment using observed data. Endpoints that are analysed untransformed and endpoints that are not formally analysed are summarized by the arithmetic mean, standard deviation (SD), minimum and maximum value with counts (N). Mean and SDs rounded to one decimal, minimum, maximum is presented exact as per the data values.

## **5.3 Other Statistical considerations**

All the statistical analysis for other tables other than endpoint results will be generated based on Implant population only. However, depending on the results and sponsor requirements the Implant population results will be performed.

### **5.3.1 Patient disposition/status**

Number of subjects enrolled by investigator and site will be summarized with counts and percent based on Implant population.

A table based on Subject Disposition of Clinical Follow-up Compliance will be provided at MRI Visit +1Month visits after device implant. A table supported to present the counts based on the enrollments per site will be provided.

If any deaths happened, a supporting listing based on deaths will be provided with related to study device and study procedure, with date of death and duration of days from device implant.

### **5.3.2 Baseline and Demographic analysis**

Baseline characteristics with Arrhythmia and Cardiac disease history, physical examinations summarized at screening or baseline visit. Continuous measurements will be summarized descriptively and categorical measurements with counts and percent.

### **5.3.3 Procedure Characteristics and performance**

Procedure evaluation summary for Atrial Fibrillation., RA, RV & LV lead measurements and PNS threshold with New Episode of polymorphic and Image Artifacts measurement are summarized. Device Information like Pulse generator, Defibrillation Lead & LV Lead are summarized for Implant populations at Implant procedure, Pre-Discharge, MNS Pre - Post MR Scan visits, Pre MR-Scan Visit, Post MR Scan Visit & MRI Visit+1 Month procedure, MRI Visit+ 3-month, MRI Visit+ 6-month, MRI

Visit+ 9-month visits and Implant+1-year visits. However, the results will be summarized only for the above available timepoint visits.

A comprehensive listing based on MRI information by visits is presented by subject with MRI protection mode, Time of MR scan initiation and completion, exiting MRI protection and radiologist scores are presented.

- A listing based on pacing threshold LEAD (RA/RV/LV) for each subject with site
- A listing based on Sensed Amplitude LEAD (RA/RV/LV) for each subject with site
- A listing based on Pacing Impedance LEAD (RA/RV/LV) for each subject with site
- A listing based on Shocking Impedance LEAD (RA/RV/LV) for each subject with site

will be presented based on available analysis time points including Implant procedure, Pre-Discharge, MNS Pre - Post MR Scan visits, Pre MR-Scan Visit, Post MR Scan Visit & MRI Visit+1 Month procedure, MRI Visit+ 3-month, MRI Visit+ 6-month, MRI Visit+ 9-month visits and Implant+1-year visits. All the above listings are based on Implant populations.

A summary table for all medications with Generic medication name summarized for cardiovascular medication usage based on Implant population presented for Implant, pre-Discharge, MR Scan, MRI Visit+1-week, MRI Visit+1-month, MRI Visit+ 3-month, MRI Visit+ 6-month , MRI Visit+ 9-month visits and Implant+1-year visits.

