### **12.7.1. Device Evaluation Prior to Commencement of MR Scan**

1. All implanted leads will be evaluated through the implanted PG for **THREE separate consecutive sets of measurements** using the test parameters listed in Table 12-3:

- Manual pacing threshold tests, as defined in sections 12.5.1.1, 12.5.1.2 and 12.5.1.3.
- Sensing amplitude
- Impedance
- Shock impedance (RV lead only)

2. Test for phrenic nerve stimulation (PNS) and measure the PNS threshold if detected in the programmed LV lead configuration
3. Perform an evaluation of Beeper function as defined in section 12.7.1.1.
4. Print the 'Quick Notes' Report

Record the measurements in the EDC system.

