### **12.8.1. Device Evaluation**

1. All implanted leads will be evaluated through the implanted PG **for THREE separate consecutive sets of measurements** using the test parameters listed in Table 12-3:
  - Manual pacing threshold tests, as defined in sections 12.5.1.1, 12.5.1.2 and 12.5.1.3.
  - Sensing amplitude
  - Impedance
  - Shock impedance (RV lead only)
2. Test for phrenic nerve stimulation (PNS) and measure the PNS threshold if detected in the programmed LV lead configuration
3. Record the measurements in the EDC system.

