**Table 12-7 MRI + 1 Month Source Documentation Requirements**

Source Documentation Requirement	Disposition
Device Evaluation (pace threshold, sense amplitude, impedance, RV shock impedance, LV Phrenic Stimulation threshold)	
PRM ECG strips from manual threshold tests documenting LOC for all implanted leads	
Printout of ‘Quick Notes’ Report	
Documentation of spontaneous VT/VF episode(s) by PRM strips, as applicable: 

• ‘Selected Episodes Report’ (counters and EGMs required)

• ‘Arrhythmia Logbook’

	Retain at center
Adverse Events	
Save All	Retain the original at the center and submit a copy to Boston Scientific

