**Table 20-1 Potential Adverse Events for Pulse Generator and/ or Lead System Implants**

Potential Adverse Events for Implantation of a Pulse Generator and/ or Lead System	
Adverse reaction to procedure (e.g., bradycardia, general, respiratory, hypotension)	Lead dislocation
Air embolism	Lead fracture
Allergic reaction	Lead insulation breakage or abrasion
Allergic reaction to the contrast media	Lead perforation
Arterial damage with subsequent stenosis	Lead tip deformation and / or breakage
Bleeding	Local tissue reaction
Bradycardia	Loss of capture
Breakage/failure of the implant instruments	Low amplitude VF signals
Cardiac tamponade	Malignancy or skin burn due to fluoroscopic radiation
Chronic nerve damage	Myocardial Infarction
Component failure	Myocardial necrosis
Conductor coil fracture	Myocardial trauma (e.g., irritability, injury, tissue damage, valve damage)
Coronary venous spasm	Myopotential sensing
Death	Oversensing / undersensing
Electrolyte imbalance/ dehydration	Pacemaker-mediated tachycardia (PMT)
Elevated thresholds	Pericardial rub, effusion
Erosion	Pneumothorax
Excessive fibrotic tissue growth	Post-shock rhythm disturbances
Extracardiac stimulation (muscle/ nerve stimulation)	Prolonged exposure to fluoroscopic radiation
Fluid accumulation	Pulse generator and/or lead migration
Foreign body rejection phenomena	Renal failure from contrast media used to visualize coronary veins
Formation of hematomas or seromas	Shunting current during defibrillation with internal or external paddles

Heart block	Syncope
Hemorrhage	Tachyarrhythmias, which include acceleration of arrhythmias and early, recurrent atrial fibrillation
Hemothorax	Thrombus, thromboemboli
Inability to defibrillate or pace	Valve damage
Inappropriate therapy (shocks, ATP or pacing)	Vasovagal response
Incisional pain	Venous occlusion
Insulating myocardium during defibrillation internal or external paddles	Venous trauma (e.g., perforation, dissection, erosion)
Incomplete lead connection with pulse generator	Worsening heart failure
Infection including endocarditis	

Subjects may develop psychological intolerance to a pulse generator system and may experience the following: dependency, depression, fear of premature battery depletion, fear that shocking capability may be lost, imagined shocking/fear of shocking while conscious, and fear of device malfunction.

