#### 7.3 Methods for Handling Missing Data

No imputation method will be performed for the missing data handling.

Missed or late visits will be recorded as Protocol Deviations.

When calculating rates of treatment-emergent adverse events, missing and partial dates will be handled as shown in the table below.

Partial Date	Action Taken
Entire adverse event onset date is missing	The procedure date will be used for the onset date.

Partial Date	Action Taken
The month and the day of the month are missing but the year is available	January 1 st will be used for the month and day of the onset date. However, if the imputed date falls before the procedure date, then the procedure date will be used for the onset date.
Day is missing, but the month and year are available	The 1 st will be used as the day of the onset date. However, if the imputed date falls before the procedure date, then the procedure date will be used for the onset date.

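### PNS threshold exists only where stimulation is detected, so the SAP's by-visit summary of it cannot be read as change, and no count of new onset is planned

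*Combined protocol and SAP*

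**What the plan says.** The protocol's MRI + 1 Month evaluation (12.8.1) asks sites to "Test for phrenic nerve stimulation (PNS) and measure the PNS threshold if detected in the programmed LV lead configuration". The same conditional instruction applies before the scan (12.7.1) and after it (12.7.4). The source-document list for the 1-month visit (Table 12-7) names only the threshold ("RV shock impedance, LV Phrenic Stimulation threshold"). Table 12-6 does the same for the MRI Visit. Neither has a separate item for stimulation present or absent.

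SAP 5.3.3 lists "lead measurements and PNS threshold with New Episode of polymorphic" among the items to be summarised. It does not say which statistics will be used. SAP 5.2 supplies a general rule: "All continuous measurements will be summarized descriptively at each visit by treatment using observed data", with mean, SD, minimum, maximum and N. SAP 7.3 adds "No imputation method will be performed for the missing data handling", and no rule covers a test in which nothing was detected.

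No section plans a PNS count, a new-onset count or a paired before/after comparison. PNS is not among the endpoints or ancillary assessments (protocol 8.2 and 8.3, SAP 3.3). The by-subject lead listings in SAP 5.3.3 cover pacing threshold, sensed amplitude, pacing impedance and shocking impedance, but not PNS.

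**The concern.** Whether stimulation is present decides who has a threshold at all. A subject without PNS before the scan and with PNS after it contributes only to the later rows. A subject whose PNS resolves drops out of them. The pre-scan and post-scan rows therefore describe different people, and the difference between their means is not a change in anyone.

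The questions this test can answer are whether stimulation appeared after the scan and whether the threshold moved within a subject. The planned summary gives neither directly, and without a PNS listing a reader of the report cannot recover them. Extracardiac stimulation is among the potential adverse events in protocol Table 20-1, so a result that the protocol collects three times around the scan should be readable.

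**Working it through.** The documents give no PNS rate or threshold, so there is no planned figure to reproduce. The check uses assumed values.

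**Inputs**
- Threshold measured only if PNS is detected: protocol 12.7.1, 12.7.4, 12.8.1.
- By-visit summary on observed data: SAP 5.2. No imputation: SAP 7.3.
- LV-lead subjects: 10 CRT-D enrolled and at most 2 lost, so 10 - 2 = 8 at the least (protocol 13.3, SAP 3.5).
- Assumed: 8 CRT-D subjects scanned, 2 with PNS before the scan at 3.0 V and 4.0 V. Both are unchanged afterwards, and one other subject has new PNS at threshold t.

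**Effect of one new case on the mean**

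With k cases of mean m, the new mean is (k·m + t)/(k + 1), so the shift is (t - m)/(k + 1). Here k = 2 and m = (3.0 + 4.0)/2 = 3.50 V.

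| t (V) | Shift = (t - 3.5)/3 | Post-scan mean (V), N = 3 |
|---|---|---|
| 2.0 | -0.50 | 3.00 |
| 3.5 | 0.00 | 3.50 |
| 5.0 | +0.50 | 4.00 |
| 6.0 | +0.83 | 4.33 |
| 7.0 | +1.17 | 4.67 |

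In every row the within-subject change is zero and one subject has new stimulation. The mean can fall, stay the same or rise.

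**What N shows**

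N moves from 2 to 3 in the table, which is visible. Two cases defeat it:
- One onset plus one resolution. If the 4.0 V subject resolves and a new subject appears at 4.0 V, the values are again 3.0 and 4.0. Mean (3.50), SD, minimum, maximum and N (2) are all identical before and after, although two of eight subjects changed status.
- Untested subjects. N = 3 among 8 fits five negative tests, or four negative tests and one missed test.

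**What a count would show for the same data** (Clopper-Pearson 95%)
- Before the scan: 2/8 = 25.0% (3.2% to 65.1%).
- After the scan: 3/8 = 37.5% (8.5% to 75.5%).
- New onset among the 8 - 2 = 6 free of PNS before: 1/6 = 16.7% (0.4% to 64.1%).
- New onset over all LV-lead subjects: 1/8 = 12.5% (0.3% to 52.7%), or 1/10 = 10% (0.3% to 44.5%) if all ten are scanned.

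**The case against.** The strongest reply has four parts.

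- **The mean is inferred.** SAP 5.3.3 says only that PNS threshold is summarised, in a sentence that mixes categorical items with measurements. Table shells and eCRF pages are not in the documents, and nothing rules out a detected/not-detected row. This stands as a limit. The SAP 5.2 rule nevertheless covers all continuous measurements, and SAP 5.3.3 makes no exception for PNS.
- **N, minimum and maximum accompany the mean.** Since a threshold exists only where PNS is detected, N is close to a count of cases, and in many scenarios a new case would be noticed. This stands in part. N is not a rate among tested subjects, and it misses the two cases worked above.
- **New PNS may be reported as an adverse event.** Adverse events are collected at every visit (Table 12-1), Table 21-3 gives a timeline for non-serious events, and SAP 5.3.4 tabulates serious and non-serious events. This also stands in part. No rule requires PNS found only on protocol testing to be reported, and the list of reportable categories in protocol 21.1 does not include non-serious events.
- **PNS affects no success criterion.** This stands in full.

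A reader might infer that the plan will conceal new stimulation, or present a new harm as an improvement. The documents do not support that. The mean rises only if the new threshold exceeds the existing mean, the accompanying statistics often reveal the extra case, and the adverse-event tables offer a second route. That a higher PNS threshold is the favourable direction is itself an assumption, as the documents do not say so.

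**Conclusion.** The concern holds as a weakness in a secondary descriptive summary. As written, the SAP would compare PNS thresholds across visits in sets of subjects selected by the outcome, and it plans no detection count, paired comparison or listing that would allow change to be read. With two existing cases at the assumed 3.0 and 4.0 V, one new case moves the mean by between -0.50 and +1.17 V for a new threshold of 2.0 to 7.0 V, with no change in any existing case. The direction is not predictable in advance.

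This rests on the SAP 5.2 rule being applied to PNS threshold and on no present/absent row being hidden in table shells outside the documents. The primary safety endpoint, the five effectiveness endpoints and the limit of two failed cases are untouched. With 8 to 10 LV-lead subjects, precision stays poor under any method: even 0/8 new onset has an upper 95% limit of 36.9%. The gain is a readable result, not a precise one.

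**What to change.** In SAP 5.3.3, replace the bare mention of PNS threshold with three outputs:

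1. PNS recorded as detected, not detected or not tested at pre-scan, post-scan and MRI + 1 Month. Present it as paired shift tables (pre-scan against each later time) over all scanned LV-lead subjects tested at both times, with new-onset n/N and an exact 95% interval. State the denominator; those tested at both times and free of PNS before the scan is the natural one. Do not restrict this table to the Implant population, the default for non-endpoint tables (SAP 5.3). That set drops subjects with a lead-related complication between the MRI Visit and MRI + 1 Month (SAP 4.1), so it could remove a new PNS case classed that way.
2. Within-subject threshold change only where PNS was detected at both times. Flag, here and in the shift tables, subjects whose programmed LV configuration changed between tests. The test uses the programmed configuration, protocol 12.7.5 allows reprogramming at the end of the MRI Visit, and the fixed-configuration requirement in Table 12-3 does not name PNS. A shift at 1 month could otherwise reflect reprogramming rather than the scan.
3. A by-subject PNS listing beside the existing lead listings.

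The cost is SAP wording, a small set of tables and one listing, with no added patients or tests. One point needs checking: the source tables name only the threshold, so the sponsor should confirm that the eCRF distinguishes a negative test from no test. If it does not, derive this from source records or add one field.
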